- A description of the subject selection criteria and rationale for selection in terms of the scientific objectives and proposed study design;
- A compelling rationale for proposed exclusion of any sex/gender or racial/ethnic group;
- Justification for the inclusion of vulnerable groups such as children, prisoners, adults with impaired consent capacity, or others who may be vulnerable to coercion or undue influence.

Please consider these resources:

[NIH Diversity Policy](#)

[FDA Diversity Guidance](#) ⓘ

Pilot study

Inclusion criteria. Potential participants will be healthy controls who are employed in and around [name]. For inclusion in the pilot, they need to be 1) 18-55 years of age; 2) male or female gender 3) Able to read, understand and communicate in English; 4) Can have a past/current history of smoking.

Exclusion criteria. Intoxication with substances on day of the study.

Study Proper

Inclusion criteria. Potential participants will be: 1) Patients enrolled in the Bluegrass Clinic; 2) 18-55 years of age; 3) male or female gender 4) Able to read, understand and communicate in English; 5) willing to adhere to the general rules of the Bluegrass Clinic/SMARTClinic/Beyond Birth Clinic; 6) willing and able to abstain from drug use other than Suboxone; 7) exhaled breath on day of study CO < 5 ppm; 8) Stabilized on maintenance buprenorphine if having comorbid opioid use disorder.

Exclusion criteria. Traumatic brain injury, history of seizure disorder, history of or current diagnosis of schizophrenia, intracranial metal shrapnel, previous adverse effect with TMS, sub-threshold consistency while performing behavioral tasks, failure to show baseline attentional bias to smoking versus neutral cues.

We will exclude pregnant females in our study due to danger of MRI radiation to the unborn fetus.

The main study is not connected to the Bluegrass HIV clinic, SMART clinic or the Beyond Birth Clinic. A person can be enrolled and receiving care at these clinics, and their participation in the research project does not impact their standing in any of these clinics. Participation is truly voluntary in nature.

Attachments

Indicate the targeted/planned enrollment of the following members of minority groups and their subpopulations. Possible demographic sources: [Census Regional Analyst Edition](#), [Kentucky Race/Ethnic Table](#), [Kentucky Population Data](#).

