74. Alcorn JL, 3rd, Strickland JC, Lile JA, Stoops WV, Rush CR. Acute methylphenidate administration reduces cocaine-cue attentional bias. *Prog Neuropsychopharmacol Biol Psychiatry*. 2020;103:109974.

Objectives

List your research objectives. Please include a summary of intended research objectives in the box below.

Before the study proper, we will conduct a pilot study to validate our attentional bias task in healthy controls who may or may not have a history of current or active smoking. The specific aim of this pilot would be to show differences in attentional bias between smokers and non smokers.

Study proper. Specific Aim 1 will demonstrate whether one session of MRI targeted TBS to left dorsolateral prefrontal cortex (DLPFC) will decrease attentional bias to smoking cues, compared to sham TMS. Subjects will receive both one TBS session (1800 pulses) and one session of sham TMS, lasting 10 minutes on separate days. They will perform an attentional bias task before and after TBS. We hypothesize that TBS will significantly decrease post session attentional bias to smoking cues compared to sham TMS.

Specific Aim 2 will demonstrate whether one session of TBS versus sham TMS, to left DLPFC can modulate stress induced craving for smoking. Subjects will perform the short form of tobacco craving questionnaire (TCQ-SF) before and after TBS. We hypothesize TBS will significantly decrease craving in smoking patients compared to sham TMS.

Specific Aim 3 will demonstrate whether one session of TBS versus sham TMS, to left DLPFC can increase seed based functional connectivity (fc) in the ventral striatum. We will acquire resting state functional MRI (fMRI) scans before and after TBS in all subjects. We hypothesize increase in fc in the dorsal anterior cingulate – ventral striatum circuit after TBS.

Study Design

Describe and explain the study design (e.g., observational, secondary analysis, single/double blind, parallel, crossover, deception, etc.).

- **Clinical Research:** Indicate whether subjects will be randomized and whether subjects will receive any placebo.
- **Community-Based Participatory Research:** If you are conducting community-based participatory research (CBPR), describe strategies for involvement of community members in the design and implementation of the study, and dissemination of results from the study.

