We will measure attentional bias using a validated database of smoking and neutral cues and Tobii Pro Fusion 120 Hz eye tracker (Tobii Technology, Sweden). Smoking and neutral cues will be presented side-by-side on the screen for 1000?milliseconds. Eye tracking will record eye movements and fixation times for both cue types. Upon offset of the cues, a visual probe ('X') will appear on either the left or right side of the computer screen. Participants will be instructed to respond as quickly as possible to the probe. The primary dependent variable will be mean fixation time (milliseconds) calculated by summing the total fixation time for each cue type and then dividing by the total number of critical trials (i.e., 40). Reaction times to the visual probe will also be collected.

Attention bias behavioral activation (ABBA) task using go/no go

A modified cued go/no-go task is used as a measure of inhibitory control. The procedures and parameters for the attentional bias-behavioral activation (ABBA) task are identical to the traditional cued go/no-go task except that opiate-related images serve as go cues and neutral images serve as no-go cues. Opiate related images and neutral images that will be used for this task are attached below.

Delayed discounting task

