Eye Tracker. The Tobii Pro Fusion housed at [name] is an exceptionally flexible remote eye tracking system offering supreme tracking performance in a wide array of human behavior research studies. This small eye tracking research system offers unprecedented portability and freedom of head movement in combination with unparalleled tracking accuracy and robust participant tracking capability. It allows for both screen and real-world test scenarios. For screen based research, it can be used with a laptop, an external monitor or an all-in-one PC. It can be mounted below most screens. With the eye tracker flush mounted on a screen, researchers can achieve highly accurate results for stimuli presentation on screens. Using a desk stand, one can track larger screens. This gives researchers the freedom to present stimuli on a screen that best meets the specific needs of the study at hand. The eye tracking system captures data up to speeds of 250 Hz (available 60, 120, 250 Hz modes). It delivers unparalleled data accuracy within the whole tracking box and very robust participant tracking capability. Robust eye tracking capability ensures very low data loss in real life conditions. The system with automatic selection of bright or dark pupil eye tracking accommodates for large variations in experimental conditions and demographic populations. The system also comes fitted with Tobii Pro Lab. This is a versatile biometric software platform designed for extensive research into human behavior using eye tracking analysis. It also has added ability to be combined with other physiological data streams. From in-store shopper research to psychology experiments, Pro Lab makes it easy for anyone to start using various biometric tools in their research in order to further expand the scope and richness of their insights. Pro Lab works well with both screen-based and wearable eye trackers.

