Each Section/Subsection in the menu on the left must have a checkmark beside it (except this Submission section) indicating the Section/Subsection has been completed. Otherwise your submission for IRB review and approval cannot be sent to the Office of Research Integrity/IRB.

If applicable, remember to update the Approval Letter Details text box under the Additional Information section

If your materials require review at a convened IRB meeting which you will be asked to attend, it will be scheduled on the next available agenda and you will receive a message to notify you of the date.

If you are making a change to an attachment, you need to delete the attachment, upload a highlighted version that contains the changes (use Document Type of "Highlighted Changes"), and a version that contains the changes without any highlights (use the appropriate Document Type for the item(s)). Do **not** delete approved attachments that are still in use.

Principal Investigator's Assurance Statement

I understand the University of Kentucky's policies concerning research involving human subjects, and I attest to:

1. Having reviewed all the investigational data from this study, including a compilation of all internal and external unanticipated problems.
2. Having reviewed, if applicable, information from the sponsor including updated investigator brochures and data and safety monitoring board reports.

I also attest that I have reviewed pertinent materials concerning the research and concluded:

- The human subject risk/benefit relationship is unaffected, mitigated, or eliminated by closure of the study and all pertinent materials for closure of the research are being submitted to the IRB for consideration.

By checking this box, I am providing assurances for the applicable items listed above.

Your protocol has been submitted.

Attentional Bias Analyses. Attentional bias for cigarette cues will be calculated separately for each set of trials, by subtracting the average fixation time on neutral cues from the average fixation time on cigarette cues. Fixation time on cigarette cues for each session and resultant cigarette cue attentional bias score will be entered into separate linear fixed effects regression models. Dependent variables for these models will be fixation time on cigarette cues and attentional bias for cigarette cues respectively.

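### Attentional bias scoring divides by a fixed 40 trials, so lost-gaze trials count as zero looking and, in expectation, shrink both Aim 1 outcomes in proportion to the loss

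*Combined protocol and SAP*

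**What the plan says.** Research Procedures, Attentional Bias task, sets the display: "Smoking and neutral cues will be presented side-by-side on the screen", for 1000 ms. It then defines the outcome: "The primary dependent variable will be mean fixation time (milliseconds) calculated by summing the total fixation time for each cue type", followed by "dividing by the total number of critical trials (i.e., 40").

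The Attentional Bias Analyses text at the end of the document forms the bias score by "subtracting the average fixation time on neutral cues from the average fixation time on cigarette cues", separately for each set of trials. It then names two outcomes: "Dependent variables for these models will be fixation time on cigarette cues and attentional bias for cigarette cues respectively". It gives no other denominator.

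The Aim 1 hypothesis under Objectives is directional: "We hypothesize that TBS will significantly decrease post session attentional bias to smoking cues compared to sham TMS".

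Two other places touch on data quality. The Eye Tracker paragraph under Resources says "Robust eye tracking capability ensures very low data loss in real life conditions", with no rate. The exclusion criteria for the study proper list "sub-threshold consistency while performing behavioral tasks", which applies to participants, has no stated threshold, and leaves the denominator unchanged. The documents supplied contain no per-trial gaze-validity rule, no minimum number of valid trials and no instruction for lost gaze.

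**The concern.** A trial in which the tracker recorded nothing usable is missing data. The stated formula treats it as an observation of 0 ms on each cue: it adds nothing to either sum but is still one of the 40. The resulting score mixes how long the participant looked with how well the tracker worked.

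Both modelled outcomes are affected. Raw cigarette-cue fixation has more to lose in milliseconds, because it is a total looking time and not a difference between two cues. At stake are the size of the Aim 1 effect in milliseconds, the noise in a study of 30 participants, and, if tracking were worse in one condition than the other, the TBS-sham comparison itself.

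**Working it through.** **Inputs from the documents.** 40 critical trials per run; bias = mean cigarette fixation minus mean neutral fixation; pre and post runs on both a TBS and a sham day; 30 participants. No power calculation, expected bias, SD or loss rate is stated for this outcome, so there is no figure to reproduce.

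**Assumed inputs.** Mean fixation of 420 ms (cigarette) and 370 ms (neutral), so a bias of 50 ms. Loss of 5% to 30%, whole trials lost, unrelated to cue type.

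**Step 1: identity.** With *v* usable trials and zeros from the rest, score(÷40) = (*v*/40) × score(÷*v*). The same factor applies to cigarette-cue fixation.

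| Trials lost | *v*/40 | Bias, ÷40 | Cigarette fixation, ÷40 |
|---|---|---|---|
| 2 (5%) | 0.95 | 50 × 0.95 = 47.5 ms | 420 × 0.95 = 399 ms |
| 4 (10%) | 0.90 | 45 ms | 378 ms |
| 8 (20%) | 0.80 | 40 ms | 336 ms |
| 12 (30%) | 0.70 | 35 ms | 294 ms |

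Dividing by *v* gives 50 and 420 ms in expectation on each row. A simulation (20,000 runs of 40 trials per loss rate, trial SD 150 ms, times limited to the 1000 ms window) gave ratios to the full-data bias of 0.949, 0.899, 0.801 and 0.700. The valid-trial mean did not shift.

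**Step 2: the TBS-sham contrast.** Take it as (post − pre on the TBS day) − (post − pre on the sham day), with no true change in bias.

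- 2 trials lost in every run: 0 − 0 = 0.
- 2 lost before and 8 after, on both days: (40 − 47.5) − (40 − 47.5) = 0. Each day shows a false fall of 7.5 ms, but the falls cancel.
- 8 lost after TBS, 2 in the other three runs: (40 − 47.5) − (47.5 − 47.5) = −7.5 ms for bias, and (336 − 399) − 0 = −63 ms for cigarette-cue fixation.
- 8 lost after sham, 2 in the other three: +7.5 and +63 ms.

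Now let the true effect be a fall of D ms, with the same loss pattern on both days and the same true baseline. The contrast becomes −(1 − post-run loss) × D: attenuated, same direction.

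**Step 3: random variation in loss.** If the proportion lost varies independently between runs with an SD of 10 percentage points (assumed), the added noise per run is 420 × 0.10 = 42 ms for cigarette fixation and 50 × 0.10 = 5 ms for bias. The contrast uses four runs, so this doubles (√4 = 2) to 84 and 10 ms per participant. Averaged over 30, that is 84/√30 = 15.3 ms and 10/√30 = 1.8 ms. An SD of 2 points gives one fifth of the per-participant noise: 16.8 and 2 ms.

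**The case against.** The strongest reply is that the formula was written for complete data. The figure 40 is the design count, the analysis text says only average fixation time, and a competent analyst might drop invalid trials anyway. That is possible, but the text does not say so. The only denominator stated is 40, and following it as written produces the zeros.

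Second, the tracker description expects very low loss. That is a general description of the equipment, with no rate for this task or population. It does mean that the 20% and 30% rows are illustrations and not forecasts.

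Third, a reader might infer that the rule builds a false treatment effect into Aim 1. The documents do not support that. The stress paradigm accompanies both the pre and the post assessments, and the TBS and sham days share one session layout in a counterbalanced crossover. Neither the stressor nor a late post run separates TBS from sham. Within-session falls cancel when both days lose data alike, and nothing in the documents shows that active stimulation loses more gaze than sham.

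Fourth, two absolute statements are tempting and too strong. The score is not too small every time a trial is lost: losing a trial with more neutral than cigarette looking can raise it, and a negative bias shrinks toward zero. Nor does a valid-trial denominator recover the true bias if loss is related to where the participant looks. The proportional result holds in expectation, for loss unrelated to cue type.

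Finally, a trial without fixation on either cue can be a real zero. That stands, and it constrains the fix.

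**Conclusion.** The point holds as a defect in a stated scoring rule that should be corrected. It is not a demonstrated bias in the TBS-sham comparison. When loss is unrelated to cue type, both outcomes shrink in expectation by the proportion of trials lost. Equal loss across runs costs only effect size in milliseconds and leaves the direction of the contrast alone; the standardised effect need not fall because of the denominator. Random variation between runs adds noise, mostly to cigarette-cue fixation. A systematic false difference requires loss that differs by condition, in which case it could mimic or mask the hypothesised decrease.

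The actual size is unknown. The 50 ms bias, the 420 ms fixation time and every loss rate above are assumptions, and the contrast in Step 2 is itself assumed because the terms of the regression model are not listed. If loss is as low as the equipment description suggests, the effect is small: 2.5 ms of an assumed 50 ms bias at 5% loss.

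**What to change.** Replace the fixed denominator with the number of critical trials that have valid gaze in that run. Define validity by whether the tracker recorded usable gaze, wherever it was directed. Valid gaze away from both cues then stays a true zero, and only tracking failures leave the denominator. A rule that required fixation on a cue would wrongly drop real zeros and inflate the mean.

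Before unblinding, set the share of the cue period that must have usable gaze for a trial to count, which also deals with partial loss within a trial, and the minimum number of valid trials per run. Report valid-trial counts by condition and time point, so that readers can see whether loss was low and balanced. If unblinding has already happened, report both scorings and label the new rule post hoc.

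The cost is a few sentences and a small change to the scoring code, with no new data collection if the gaze recordings are kept. The downside is that runs with few valid trials give noisier scores, or are dropped under the minimum-trial rule, and a dropped run weakens that participant's within-subject comparison.

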The TMS Suite is housed within the department of psychiatry ([name]) at the University of Kentucky, Lexington. Currently it encompasses one experimental room covering about 600 sq feet on the second floor. We are in the process of purchasing a MagPro X100 stimulator (MagVenture Inc, Atlanta, GA) with booster option and active cooling. The room will also be equipped with a laptop and a chair to provide TMS. The device is capable of producing rTMS over a wide range of parameters such as paired-pulse, theta burst stimulation, and both monophasic and biphasic waveforms. The machine weighs 35 kg and the cart encompassing the machine weighs 16 kg. Dimensions of the machine are 210 x 530 x 400 mm. We are also in the process of purchasing a frameless stereotaxic system (Brainsight Frameless, Rogue Research, Montreal, QC, Canada) for co-registration of TMS coil position on the scalp with underlying cortical anatomy on the individual subject's three-dimensionally rendered MRI scan. This permits navigation of the TMS coil to target cortical structures. Participants are administered TMS in a customized chair for stabilization of head and coil position. A coil holder especially designed for TMS ensures stable coil positioning. The Brainsight Neuronavigation system has three main components: (1) NDI Spectra infrared camera system, (2) stimulator, (3) chair with neck rest. The TMS coil is targeted to a user defined location selected on the individual 3-D Anatomical MRI with fMRI or PET data overlay with less than one millimeter error. The TMS coil is attached to a stimulator unit, which administers the TMS pulses to modulate brain function in a spatially and temporally precise fashion. The subject reclines in the chair and wears a headband equipped with a subject position tracker. The ceiling mounted infrared stereo camera detects the 3-D position of the subject tracker and also the coil position tracker, and continuously feeds this information into the control center software.

Eye Tracker. The Tobii Pro Fusion housed at [name] is an exceptionally flexible remote eye tracking system offering supreme tracking performance in a wide array of human behavior research studies. This small eye tracking research system offers unprecedented portability and freedom of head movement in combination with unparalleled tracking accuracy and robust participant tracking capability. It allows for both screen and real-world test scenarios. For screen based research, it can be used with a laptop, an external monitor or an all-in-one PC. It can be mounted below most screens. With the eye tracker flush mounted on a screen, researchers can achieve highly accurate results for stimuli presentation on screens. Using a desk stand, one can track larger screens. This gives researchers the freedom to present stimuli on a screen that best meets the specific needs of the study at hand. The eye tracking system captures data up to speeds of 250 Hz (available 60, 120, 250 Hz modes). It delivers unparalleled data accuracy within the whole tracking box and very robust participant tracking capability. Robust eye tracking capability ensures very low data loss in real life conditions. The system with automatic selection of bright or dark pupil eye tracking accommodates for large variations in experimental conditions and demographic populations. The system also comes fitted with Tobii Pro Lab. This is a versatile biometric software platform designed for extensive research into human behavior using eye tracking analysis. It also has added ability to be combined with other physiological data streams. From in-store shopper research to psychology experiments, Pro Lab makes it easy for anyone to start using various biometric tools in their research in order to further expand the scope and richness of their insights. Pro Lab works well with both screen-based and wearable eye trackers.

Magnetic Resonance Imaging and Spectroscopy Center (MRISC). The Magnetic Resonance Imaging and Spectroscopy Center (MRISC) is a service and consultation center supporting basic and clinical research at the University of Kentucky. The Center includes an advanced 3T Siemens PRISMA scanner with high performance gradients, echo-planar whole body imaging and hydrogen spectroscopic capabilities for both human and animal studies. For dedicated animal studies, a modern Bruker/Siemens 7T MR scanner has recently been installed. Recently renovated facilities for animal handling, preparation and care are available immediately adjacent to the 7T imager. There are also computing facilities, electronic and fabrication shops, and a multi-user laboratory available to support magnetic resonance and spectroscopy studies. Scientific and technical personnel are available to help in developing MR

sequences and procedures as well as to help with image-processing analysis. The Center has multiple ongoing research projects at <https://www.research.uky.edu/magnetic-resonance-imaging-and-spectroscopy-center/human-research-projects>.

In 2017 the MRISC was awarded an NIH grant to upgrade its human MRI scanner from a Siemens TIM TRIO 3T to a Siemens MAGNETOM Prisma 3T. The Prisma 3T offers maximum performance under prolonged high-strain conditions and delivers improved resolution over the previous system by coils with the highest gradient strength currently available on the market. Of note, data collected with the Prisma 3T scanner are to a higher-quality standard and are therefore more attractive for inclusion into NIH-supported neuroimaging repositories, such as the Neuroimaging Informatics Tools and Resources Clearinghouse (NITRC) and the Human Connectome Project (HCP). The Prisma 3T is equipped with a full complement of coils, updated image processing using Siemens Software 3D rendering, image fusion, perfusion, DTI fiber tracking, spectroscopy, volume rendering, shaded surface display, multiplanar reconstruction, and maximum intensity projection.

Ancillary Equipment in MRI Suite. 1) Applied Sciences Laboratories, Inc. Model 504LRO (long range optics) eye tracker complete with Real Eye software; 2) AVOTEC, Inc. Silent Vision SL-6011 LCD projection system used with Psychology Software Tools, Inc. visual presentation software, EPRIME; 3) MRA, Inc. 10 channel, fiber optic, patient response system with trigger interface and visual/auditory patient monitoring; 4) Current Designs, Inc. patient response fORP Interface Unit with 12 fiber optic cables and an MRI compatible, handheld, trackball mouse; 5) Medrad, Inc. SHS200 Power Injector; 6) InVivo Research, Inc. Precess MRI compatible patient monitor with wireless digital SPO2, ETC02, heart rate and blood pressure recording; 7) Full suite of physiological monitoring equipment from S.A. INC for small animal imaging; and 8) Microcapstar Capnograph CO2 Analyzer and MRI-1ventilator from CWE instruments for small and medium sized animals.

Computing and Data Management. The following centralized computer and file server equipment is located in the MRISC and available (1) Server, Linux, 4U Rack mounted Dell PowerEdge 6850, 64bit - 4 Quad Core Xeon Tulsa, 16GB RAM, 1.5TB SAS RAID 5 array; (2) Two Disk Array, 3U Rack mounted Dell MD1000 Power Vault, 4.5TB SAS RAID 5 array; (3) Tape Backup, 2U Rack mounted Dell TL2000, 24 x 800GB/1.6TB cartridges; (4) Network Attached Storage (NAS), 1U Rack mounted NetGear, 2.0 TB SATA RAID 5 array; (5) Dell full size 4210 rack (42U slots total; 16U slots occupied including APC; 26U slots available).

All computers and servers are protected with power supply backup and surge protecting UPSs. All MRI scans are sent to the NAS backup server immediately after the imaging session and burned to CD for permanent archiving. The MRI scanner host computer is connected to the Dell rack, containing equipment items 1-4, by 1 GB/sec fiber optic cable while the rest of the computers are connected by Cat 5e cable on a 100 MB/sec network. Institution-wide upgrades to Cat 6a network cable are currently underway. Daily incremental tape backups are made from all data on all the servers, the NAS, and the MD1000 using Yosemite Backup software running on the Poweredge 6850. Full monthly tape backups are made and stored offsite. All computers and servers are behind the UK Medical Center firewall, have individual firewalls, are accessible only with valid usernames and passwords, and have automated operating system software updating.

Bluegrass Care Clinic for HIV. The Bluegrass Care Clinic, located in Lexington, Kentucky provides HIV care, case management and psychiatric services for PLWHA in the north central Kentucky region. Currently, the clinic provides care to 1700 unique PLWHA. Approximately 175 new unique clients enroll in the clinic each year. Seventy percent of people receiving care at the Bluegrass Clinic self-report smoking cigarettes, 97% receive a prescription for anti-retroviral medication and 93% remain virally suppressed. In the Bluegrass Care Clinic there are approximately 1073 unique PLWHA, engaged in care who smoke. If we conservatively assume 1/2 may be ineligible for the study or chose not participate in the study, there are still over 500 eligible people to recruit for the study. This is nearly 2.5 times the number of people we would need to recruit (n=240) over the course of five years of the grant, if funded. These patients identify as male (81%), (18%) and transgender (1%).

The Supportive Medication Assisted Recovery Program (SMART) aims to comprehensively assess evaluation and treatment needs of patients with substance use disorders. It is housed at [name] and associated with the University of Kentucky. This clinic provides pharmacotherapy and psychotherapy treatment options for these patients in addition to urine drug screens and breathalyzer tests. Having 2 full time psychiatrists, 1 psychologists and 2 social workers on all days of the week, the clinic seeks to become a leader in integrative care in the state of Kentucky.

Potential Risks & Benefits

Risks

- Describe any potential risks – including physical, psychological, social, legal, ability to re-identify subjects, or other risks. Assess the seriousness and likelihood of each risk.
- Which risks may affect a subject's willingness to participate in the study?
- Describe likely adverse effects of drugs, biologics, devices or procedures participants may encounter while in the study.
- *Qualitative research* - describe ethical issues that could arise while conducting research in the field and strategies you may use to handle those situations.
- Describe any steps to mitigate these risks.

Benefits

- Describe potential direct benefits to study participants – including diagnostic or therapeutic, physical, psychological or emotional, learning benefits. This cannot include incentives or payments.
- State if there are no direct benefits.
- Describe potential benefits to society and/or general knowledge to be gained.

Describe why potential benefits are reasonable in relation to potential risks. If applicable, justify why risks to vulnerable subjects are reasonable to potential benefits.

The pilot study does not entail any additional risks, in addition to those already discussed for the study proper.

Study Proper. Seizure is a theoretical risk with TMS. In the Rossi et al. report it was stated that "The occurrence of seizures has been extremely rare, with most of the few new cases receiving rTMS protocols exceeding previous guidelines, often in patients under treatment with drugs which potentially lowered the seizure threshold." As Rossi et al. delineate, "rare" means that 16 cases (out of tens of thousands of rTMS sessions over the last two decades) of seizure related to rTMS have been reported. Eight occurred before safety parameters were established in 1997. Of the other eight reports, six occurred either when the safe rTMS parameters were exceeded or other safety guidelines ignored, and the actual occurrence of a seizure has been questioned in the other two (i.e., convulsive syncope or pseudoseizure may have occurred). In a workshop convened by the National Institute for Neurological Disorders and Stroke (NINDS) in 1996, researchers in the field agreed upon a set of rTMS consensus safety guidelines, including recommended stimulation parameters and contra-indications, and these consensus guidelines have been recently updated (Rossi et al., 2009). Widespread adherence to the 1996 guidelines has resulted in the virtual elimination of inadvertent seizures in rTMS studies (Rossi et al., 2009). Theta burst stimulation (TBS) that we will use in this study has been documented to be extremely safe. The risk of seizure with TBS is 0.1% (Rachid, 2017). There has been only one seizure instance reported with continuous TBS in a subject with no previous history of epilepsy but was sleep deprived after a long flight (Oberman and Pascual-Leone, 2009).

The most commonly reported side effect of rTMS is headache. This headache is typically of a muscle-tension type. It usually develops during or immediately after the stimulation and may last for minutes to hours following the end of the stimulation. It is typically limited to the day of stimulation, and usually responds promptly to single doses of over the counter pain medications. Neck pain or scalp pain may also occur. Both are usually managed easily with over-the-counter analgesics.

As noted in Rossi et al. (2009), Loo and colleagues reported mild and transient changes in auditory threshold in two depressed patients following a 2-4 week rTMS course of rTMS (16). Cases of tinnitus have been reported after rTMS treatments. In addition, recently in a study investigating the effects of rTMS on symptoms of depression, a patient experienced moderate to severe tinnitus after an rTMS session in which earplugs were not used. Rossi et al. recommended that hearing protection always should be worn during rTMS application, and that individuals with cochlear implants not receive rTMS. In the current study, earplugs will be worn by all subjects during rTMS procedures. Individuals with cochlear implants will be excluded from participation.

Risks to the unborn children of pregnant women receiving rTMS are unknown. Pregnant women will be excluded in this study. If sexually active, the subject must agree to use appropriate contraceptive measures for the duration of the study. Medically acceptable contraceptives include: (1) surgical sterilization (such as a tubal ligation or hysterectomy), (2) approved hormonal contraceptives (such as birth control pills, patches, implants or injections), (3) barrier methods (such as a condom or diaphragm) used with spermicide, or (4) an intrauterine device (IUD). Contraceptive measures such as Plan B (TM), sold for emergency use after unprotected sex, are not acceptable methods for routine use. If the subject has any uncertainty about whether they could be pregnant, another urine pregnancy test will be performed before they can participate in this protocol.

